During the home visits, the nurse establishes rapport with the mother (and father or other family members, when possible), provides brief education about infant care, parenting and child development (organized as 20 "teaching moments"), and assesses health and psychosocial risk in each of 12 domains: parenting/childcare (child care plans, parent-infant relationship, and management of infant crying), family safety (maternal supports, family violence, past maltreatment), parent mental health (depression/ anxiety, substance abuse, emotional support), and health care (parent health, infant health, and health care plan). A score of 1 (low risk) in a particular area requires no further intervention. With a score of 2 (moderate risk), the nurse delivers a brief intervention on the topic, usually consisting of 1 to 3 sessions. For a score of 3 (high risk), the nurse uses motivational interviewing – an evidence-based approach to behavioral change – to connect the family with community resources appropriate to meet the identified need (e.g., mental health counseling, financial resources or treatment for substance abuse). A score of 4 (imminent risk) requires emergency intervention. The nurse makes a final visit or phone call 4 weeks after completing the case, to reinforce community connections.

Dodge and colleagues randomly assigned every (even /odd) hospital birth in Durham County, North Carolina over a period of 18 months (N = 4777). They reported a Family Connects participation rate of 80% of the community population of families of newborns and 84% fidelity to the Durham Family Connects protocol. Hospital records were analyzed using an intent-to-treat approach to evaluate impact among a representative subset of 549 families.

Dodge et al. (2013) found that families assigned to intervention had 50% less total emergency department use across the first 12 months of life, controlling for demographic factors. They concluded that nurse home visiting can be implemented universally at high fidelity with positive impacts on infant emergency department usage that are similar to those of longer, more intensive home visiting programs. This approach was viewed as offering a novel solution, achieving population-level impact through an individually tailored intervention.

The proposed study will be the first RCT of the Family Connects program outside of Durham, NC.

2 **If available, upload your applicable literature search:**

Name	Created	Modified Date

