## Sample Size and Data Analysis

**If you uploaded a separate research protocol document in the 'Research Protocol' page, cite the applicable section and page numbers from that document in the answer boxes below.**

1 \* Provide the rationale and sample size calculations for the proposed target population:  
Following guidelines established by Cohen (1988) and using Gpower software (Faul et al., 2009), power analyses estimating at least 0.80 power and a significance level of 0.05 indicated that a sample size of 400 (assuming equal groups) will detect small to medium effects in most of the outcomes of interest. Some outcomes are more exploratory in nature. In addition, it is possible that additional research funding garnered in the course of this study will allow for an increased sample size.

2 \* Provide the plan for data analysis. Include in the description the types of comparisons that are planned (e.g., comparison of means, comparison of proportions, regressions, analysis of variance, etc.), which is the primary comparison/analysis, and how the analyses proposed will relate to the primary purposes of the study:  
The principal independent variable will be MFC group (MFC participant/non-participant). The dependent variables of interest will be (a) infant emergency room use and overnight hospital stays; (b) family use of community resources and child care; (c) maternal wellbeing; and (d) quality of the home environment. We will also explore long-term differences between MFC and non-MFC participants in (a) rates of official investigations for child maltreatment and (b) two indicators of early educational achievement: kindergarten readiness scores and rates of kindergarten attendance.

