Effects of Early Community Services on Child and Family Development

ClinicalTrials.gov Identifier: NCT04019977

Last updated: July 18, 2023

Statistical Analysis Plan

The principal independent variable will be MFC group (MFC participant/non-participant). The dependent variables of interest will be (a) infant emergency room use and overnight hospital stays; (b) family use of community resources and child care; (c) maternal wellbeing; and (d) quality of the home environment. We will also explore long-term differences between MFC and non-MFC participants in (a) rates of official investigations for child maltreatment and (b) two indicators of early educational achievement: kindergarten readiness scores and rates of kindergarten attendance.

A two-tailed intent-to-treat design analysis will include all randomly assigned families (regardless of actual intervention participation). Ordinary least squares regression models will be used to estimate impact of MFC on continuous and categorical outcomes. Poisson regression models will be used for count variables with skewed distribution. Covariates for all models will include the following: Medicaid status (yes/no) at birth and at 6 months, mother race/ethnicity (nonminority/minority), single parent household (yes/no), birth complications (yes/no) including maternal health conditions affecting the baby, infant injuries from birth trauma, and infant distress. Exploratory moderators will include infant birthweight, family Medicaid status, and mothers' adverse childhood experiences and adult attachment security. All results will be analyzed at the .05 significance level.

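### Counts are to be analysed by Poisson regression with no allowance for overdispersion; if the counts are overdispersed, ordinary standard errors give a false-positive rate above .05

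*SAP*

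**What the plan says.** The second paragraph of the SAP assigns ordinary least squares to continuous and categorical outcomes and then gives its only rule for counts: "Poisson regression models will be used for count variables with skewed distribution". The Protocol (Sample Size and Data Analysis, item 2) carries the same sentence and adds nothing to it.

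Testing is two-sided and by assigned group: "A two-tailed intent-to-treat design analysis will include all randomly assigned families". The threshold is common to all outcomes: "All results will be analyzed at the .05 significance level". Adjustment is also common: "Covariates for all models will include the following: Medicaid status (yes/no) at birth and at 6 months", followed by minority status, single-parent household and birth complications.

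Neither document names a variance estimator, a dispersion check or parameter, or a fallback model for counts. Neither says which outcomes are counts. The natural candidates come first in the Protocol's outcome list: "a) infant emergency room use and overnight hospital stays". No mean, variance or event rate is given for them. The sample-size statement is that "a sample size of 400 (assuming equal groups) will detect small to medium effects", with no separate calculation for a count outcome.

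**The concern.** A Poisson model fixes the variance at the mean. Its ordinary, model-based standard errors inherit that assumption, conditional on the covariates. Health-service use by infants may not satisfy it: if some families have a higher underlying rate and the covariates do not capture this, the variance exceeds the mean. The estimated rate ratio remains usable, but its standard error is too small.

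At stake are the interval width and the error rate for what may be the most closely read outcomes. The Protocol's Supporting Literature describes reducing infant injury and emergency care in the first year as a primary goal of the programme. A test run as plain Poisson could be declared significant at .05 when its real false-positive rate is higher. Because the variance estimator is not stated, it could also be chosen after results are known.

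**Working it through.** **Inputs from the documents.** Two-sided .05; 400 families in equal groups, so 200 per arm; Poisson regression with five binary covariates. **Inputs that must be assumed.** Mean count, dispersion, covariate prevalences, and how far covariates predict risk.

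**1. The plan's own figures.** With 200 per arm, 80% power is reached at a standardised difference of (1.960 + 0.842) × √(2/200) = 0.28. That is compatible with a small-to-medium effect, but 400 cannot be strictly reproduced because no effect size is stated. It also says nothing about counts.

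**2. Error of the ordinary Poisson test.** Let φ be the variance-to-mean ratio after covariates. The true standard error is √φ times the model-based one, so

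type I error = 2 × [1 − Φ(1.96/√φ)].

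At φ = 1 this gives 2 × [1 − Φ(1.96)] = 5.0%: the stated level holds.

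**3. An illustrative range for φ.** Suppose a share p of families has r times the event rate of the rest, with overall mean m. The lower rate is b = m/(1 − p + pr), the variance of the rates is p(1 − p)(r − 1)²b², and φ = 1 + that variance/m. The grid was p = 10%, 20%, 30%; r = 3, 4, 5; m = 0.4, 0.8.

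- Lowest (p = 10%, r = 3, m = 0.4): b = 0.4/1.2 = 0.333; variance = 0.09 × 4 × 0.111 = 0.040; φ = 1 + 0.040/0.4 = 1.10.
- Highest (p = 20%, r = 5, m = 0.8): b = 0.8/1.8 = 0.444; variance = 0.16 × 16 × 0.1975 = 0.506; φ = 1 + 0.506/0.8 = 1.63.

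| φ | 1.96/√φ | Type I error | Factor by which intervals should widen (√φ) |
|---|---|---|---|
| 1.00 | 1.96 | 5.0% | 1.00 |
| 1.10 | 1.87 | 6.2% | 1.05 |
| 1.63 | 1.54 | 12.5% | 1.28 |

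**4. Do the covariates remove the problem?** Null trials were simulated with 200 per arm, treatment plus five binary covariates fitted, and 20,000 replicates per cell. Each entry is ordinary versus robust type I error.

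| Mean, share, ratio | Covariates unrelated to risk | Four covariates, odds ratio 2 each | Four covariates, odds ratio 5 each |
|---|---|---|---|
| 0.4, 10%, 3 | 5.9% v 5.0% | 6.1% v 5.0% | 6.1% v 5.2% |
| 0.4, 20%, 5 | 9.0% v 5.3% | 8.1% v 5.0% | 7.7% v 5.1% |
| 0.8, 10%, 3 | 7.4% v 5.2% | 7.1% v 5.1% | 7.0% v 5.1% |
| 0.8, 20%, 5 | 12.6% v 5.2% | 12.6% v 5.3% | 10.5% v 5.0% |

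Strong covariates reduce the excess but do not remove it. Twelve further mixture cells gave 5.8% to 11.8% for ordinary errors and 4.8% to 5.2% for robust errors. Simulated interval widening after covariates was 1.04 to 1.27.

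**5. How good is the remedy?** With negative binomial counts and the same covariates, robust errors gave 4.7% to 5.5% at means 0.2 to 0.8 and φ from 1 to 2. The limit appears with rare, strongly overdispersed counts. In a group-only model at φ = 3 (40,000 replicates), robust errors gave 6.4% at mean 0.2, 7.0% at mean 0.1 and 8.0% at mean 0.05. Ordinary errors gave 25.2%, 24.4% and 22.1%.

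Pearson-scaled errors were compared with robust errors in two further group-only checks. At means 0.3 to 1.0 and φ from 1.25 to 3, scaled errors gave 4.9% to 5.4% and robust errors 5.1% to 5.8%. At φ = 3, scaled errors gave 5.2% at mean 0.2, 4.7% at mean 0.1 and a conservative 2.8% at mean 0.05.

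**The case against.** **The plan does not prescribe model-based errors.** Poisson regression with robust or scaled errors already complies with the sentence, so nothing stated is wrong. This stands as far as it goes. But Poisson regression named without qualification ordinarily means model-based errors, and the plan gives no direction away from them.

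**Overdispersion is not shown.** This stands in full. A reader might infer it from the nurses' risk scale in the Protocol's Supporting Literature, which runs from low to imminent risk. That scale describes how the programme sorts families' needs. It does not say how many families fall at each level or how their emergency visits vary, so it is not evidence about the counts.

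**Skewness as the criterion.** A reader might also infer that the plan uses skewness as its check on the Poisson variance, and so relies on the wrong test. The text does not support that. The sentence follows the least-squares rule and naturally says when an outcome leaves least squares for a count model. Skewness is reasonable for that purpose, and nothing presents it as a comparison of variance with mean.

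**The assumed means may be off.** The documents contain both a 6-month interview and records to age 6 years, and tie neither to a count. True means could lie outside 0.4 to 0.8 in either direction. This stands, and it is why the result is given as a range.

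**Sandwich errors are not the only remedy.** This also stands. Pearson scaling performed as well or slightly better in most settings checked, and either would do.

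**Conclusion.** The concern holds conditionally. It is certain that the only rule for counts makes no provision for variance above the mean. Whether that does harm depends on two conditions: the counts are overdispersed after covariates, and ordinary errors are used. Under both, type I error is about 6% to 13% at assumed ratios of 1.1 to 1.6. The low end is close to nominal; the high end is more than twice the stated level. At a ratio of 1 there is no problem.

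The dispersion range, mean counts and covariate prevalences are all assumptions, since the documents supply none. The documents do not support reading this as proof that the trial's error rate will be inflated. Larger ratios (for example 2 or 3, where the formula gives 17% and 26%) are a sensitivity range only. The point is still worth acting on, because the protection costs almost nothing and should be fixed before the outcomes are analysed.

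**What to change.** In both the SAP (second paragraph) and the Protocol (Sample Size and Data Analysis, item 2), keep the existing sentence with its skewness condition, "Poisson regression models will be used for count variables with skewed distribution", and add at its end: *with robust (sandwich) standard errors; negative binomial regression will be a sensitivity analysis.* Naming Pearson-scaled errors instead would be an acceptable equivalent, provided one is chosen in advance.

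The cost is one added clause in two places and one extra analysis in standard software. Design, data collection and sample size do not change, and robust errors leave the Poisson rate-ratio estimate as it is. Intervals become wider when counts are overdispersed, by the 1.05 to 1.28 shown above, which means less apparent precision than ordinary errors would report. When variance equals the mean the widening is essentially nil. For very rare, strongly overdispersed counts robust errors can still run at 7% to 8%, so a result for such an outcome should be read with the sensitivity analysis beside it.

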Hospital, both located in Baltimore, MD. For the purposes of this study, Sinai Hospital will serve as the community/catchment area. Nurse home visitors recruit these new mothers while they are still in the hospital/maternity ward. Following Dodge et al. (2013; 2014), when the [REDACTED] officially begins, nurse home visitors will enroll new mothers into MFC every other day only (on odd dates). Those new mothers who are not City residents and/or give birth on an even date will not be offered MFC. They will be considered the "control" group and are expected to access community services as they normally would. [REDACTED] staff will recruit ALL Baltimore City residents who give birth at Sinai Hospital, regardless of odd/even birth date, while they are still in the hospital/maternity ward and with post-discharge outreach. If a mother who gives birth on an odd date declines the MFC program, she will still be recruited into the research study. Given that the effects of MFC are a key study question, and MFC is being provided on a random-assignment basis according to child birthdate, this study follows a RCT design. At the same time, we note that its approach is different than many RCT's, in that prospective research participants are not being explicitly invited to be randomized.

3 \* **Describe the relevant prior experience and gaps in current knowledge. Describe any relevant preliminary data:**  
 While nurse home visiting programs have been shown to be effective in reducing infant injuries and improving outcomes for children and families, Family Connects is the first nurse home visiting program to be implemented on a community-wide scale. Evaluations of the Family Connects Program has been conducted by Dodge and colleagues in Durham, North Carolina (Dodge et al., 2013; 2014), demonstrating positive effects such as reduced infant emergency room use and overnight hospital stays, increased families' use of community resources, and improved family well-being. No randomized controlled trials of Family Connects have occurred outside of North Carolina, however. The proposed study seeks to expand the research on the Family Connects Program and assess its outcomes in a mid-sized, mid-Atlantic city.

4 \* **Provide the scientific or scholarly background, rationale, and significance of the research and how it will add to existing knowledge:**  

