## Supporting Literature

1 \* **Provide a summary of current literature related to the research: *If you uploaded a separate research protocol document in the 'Research Protocol' page, cite the applicable section and page numbers from that document in the answer box below.***

Family Connects is a universal nurse home visiting program designed by Dodge and colleagues at Duke University (Dodge et al., 2013; 2014). Family Connects is the first program of its kind to be implemented on a community-wide scale. Family Connects was developed as a brief, universal, postnatal nurse home visiting intervention intended to screen for risk, provide brief intervention, and connect families with more intensive evidence-based services as needed. Family Connects is not intended to be a substitute for intensive programs or services, but is meant to serve as a universal screening to ensure that families are matched with services within their own communities that most appropriately meet the identified needs. A primary goal of Family Connects is to reduce the incidence of infant injury and use of emergency medical care in the first year of life.

Family Connects is available to every family in the designated catchment area. Once screening has occurred, however, families with higher needs are triaged and referred to appropriate services.

Family Connects is highly structured and consists of 3 to 7 scripted in-person or telephone contacts, with the first contact is at the hospital immediately following the infant's birth followed by 1 to 3 nurse home visits when the child is 3 to 8 weeks old, 1 or 2 nurse contacts with community service providers and/or maternal and infant health care providers, and an in-person or telephone follow-up conversation 1 month later.

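### Every model adjusts for Medicaid status at 6 months, a post-assignment variable, so the MFC coefficient need not be the intent-to-treat effect

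*SAP*

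**What the plan says.** The second paragraph of the SAP sets the covariates: "Covariates for all models will include the following: Medicaid status (yes/no) at birth and at 6 months", followed by race/ethnicity, single-parent household and birth complications. The Protocol has the same sentence under Sample Size and Data Analysis, item 2, so this is a planned choice and not a slip in one document. It covers all models. Neither document justifies the 6-month term, says that MFC is expected to leave coverage unchanged, or plans a model without it.

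The same paragraph defines the analysis: "A two-tailed intent-to-treat design analysis will include all randomly assigned families (regardless of actual intervention participation"). The models are there to measure the programme's impact: "Ordinary least squares regression models will be used to estimate impact of MFC on continuous and categorical outcomes", with Poisson regression for skewed counts.

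The Protocol fixes the order of events. Under Justification, Objective, & Research Design, "MFC is being provided on a random-assignment basis according to child birthdate". Under Supporting Literature, the programme includes "1 to 3 nurse home visits when the child is 3 to 8 weeks old", with a follow-up contact one month later. The research interview is at about 6 months.

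Two other terms have no stated time point: single-parent household among the covariates, and the Medicaid moderator in "Exploratory moderators will include infant birthweight, family Medicaid status".

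**The concern.** In an intent-to-treat comparison the coefficient on assignment should carry the whole effect of being assigned, whatever its route. Adjusting for variables fixed at or before birth preserves that. Adjusting for something measured after the intervention does not in general, for two reasons:

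- **Part of the effect is removed.** If MFC changes coverage and coverage changes the outcome, holding coverage constant takes that part out of the MFC coefficient.
- **A spurious effect is added.** If MFC changes coverage, and an unmeasured factor such as household resources drives both coverage and the outcome, then families with the same 6-month coverage are no longer comparable across arms. A difference can appear where MFC has no effect.

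An effect of MFC on coverage is plausible. Under Supporting Literature, the domains the nurse assesses include "health care (parent health, infant health, and health care plan"), and for high-risk families the nurse works to "connect the family with community resources appropriate to meet the identified need (e.g., mental health counseling, financial resources or treatment for substance abuse"). That MFC moves Medicaid enrolment is an inference, however; the documents do not say so.

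At stake is whether each reported MFC coefficient estimates the declared quantity. The untimed moderator raises the same question: with two Medicaid time points in the plan, a reader cannot tell which defines the subgroup.

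**Working it through.** **Inputs from the documents.** Total sample 400 in equal groups, two-sided 0.05, power at least 0.80 (Protocol, Sample Size and Data Analysis, item 1). The effect size is given only in words, as small to medium.

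**Scale.** With no numeric effect size the sample size cannot be derived forward, so I solved for the detectable difference. In SD units the standard error is √(2/200) = 0.10, and the detectable difference is (1.960 + 0.842) × 0.10 = 0.280 SD. This agrees with the plan's wording.

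**Formula.** In a linear model, the MFC coefficient with the 6-month term minus the coefficient without it equals −δ × γ. Here δ is the effect of MFC on 6-month Medicaid and γ is the coefficient of 6-month Medicaid in the full model. If δ = 0 the difference is zero. With δ = 0.05 and γ = 0.3 it is −0.015; with δ = 0.10 and γ = 0.5 it is −0.050.

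**Assumed inputs.** The documents give neither δ nor γ. The simulation used 4,000,000 families (Monte Carlo error about 0.001 SD):

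- U ~ N(0,1), unmeasured; T ~ Bernoulli(0.5), assignment.
- Medicaid at birth: logit P(M0 = 1) = 0.4 + 0.8U (prevalence 59%).
- Medicaid at 6 months: logit P(M6 = 1) = −0.6 + 1.8·M0 + 0.8U + e·T.
- Outcome: Y = bU·U + bM·M6 + N(0,1), with effects divided by SD(Y).

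Setting e = 0, 0.3, 0.6, 1.0 gives 6-month coverage of 58.5% in control against 58.5%, 63.5%, 68.3% and 74.2% under MFC: shifts of 0, 5, 10 and 16 points.

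**Results.** OLS coefficient on T in SD, for shifts of 5, 10 and 16 points. Departures were taken before rounding.

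| Scenario | Birth Medicaid only | Birth and 6 months | Departure |
|---|---|---|---|
| A: bU = 0.5, bM = 0 | −0.001, −0.001, −0.001 | −0.015, −0.029, −0.045 | −0.014, −0.028, −0.045 |
| B: bU = 0, bM = −0.3 | −0.015, −0.029, −0.047 | 0.000, 0.000, 0.000 | +0.015, +0.029, +0.047 |
| C: bU = 0.5, bM = −0.3 | −0.014, −0.027, −0.043 | −0.015, −0.029, −0.046 | −0.001, −0.002, −0.003 |
| D: bU = 0.5, bM = +0.3 | +0.012, +0.025, +0.040 | −0.015, −0.028, −0.044 | −0.027, −0.053, −0.084 |

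With no coverage shift the two models agree within 0.0001 SD in all four scenarios.

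- **A** is a pure artefact, since MFC has no effect. Divided by 0.10, the departures are 0.14, 0.28 and 0.45 standard errors, and type I error is 0.052, 0.059 and 0.073 instead of 0.05.
- **B** removes a real, small effect entirely.
- **C** shows the two routes nearly cancelling.
- **D** shows them adding up, enough to reverse the sign of a small effect.

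**Power.** For a departure b toward the null at a true effect of 0.280 SD, power is Φ((0.280 − b)/0.10 − 1.960). For b = 0, 0.015, 0.030 and 0.045 this gives 80%, 76%, 71% and 65%. A departure away from the null would inflate the apparent effect instead.

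**Cross-check.** A second simulation used a linear coverage model, a total effect of 0.28 and shifts of 0, 5 and 10 points. The birth-only model returned 0.28 throughout, within simulation error. Adding the 6-month term changed nothing at zero shift. At 5 to 10 points, with a Medicaid effect of 0.3 to 0.5, the change was −0.015 to −0.050 without an unmeasured factor and −0.024 to −0.068 with one. With an unmeasured factor but no Medicaid effect it was −0.008 and −0.018.

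**The case against.** The strongest case against is that the harm is conditional and small. No passage says MFC enrols families in Medicaid. The description of the nurse's work comes from a summary of the programme model, and the link to financial resources is one example offered to high-risk families. A 16-point shift is a lot for a brief screening and referral programme: at the 80% participation reported for the earlier trial, it needs 16/0.80 = 20 points among participants. At 5 to 10 points, type I error in scenario A is at most 0.059, scenario C nearly cancels, and only D exceeds half a standard error. All of this stands, and it limits the size claimed. It does not give a reason to keep the term.

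The figures are for OLS, while emergency room use and overnight stays may be analysed by Poisson regression. That also stands: no size has been worked out for those models, though the structural argument carries over.

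Two further points are separate. Consent is taken only at the 6-month assessment, and the SAP labels the main independent variable by participation, not assignment. Either could undermine the intent-to-treat claim even after this change, but neither makes the covariate sound.

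Finally, the SAP is dated July 18, 2023. Recruitment was planned to end on January 14, 2021, so 6-month interviews would have finished around July 2021. Dropping a prespecified covariate that late needs a dated, reasoned amendment. This is a fair procedural point and is taken up in the fix.

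**Conclusion.** The concern holds. The plan conditions every model on a variable measured after assignment and after the home visits while declaring an intent-to-treat analysis, so the MFC coefficient is not guaranteed to be the total effect of assignment. That conclusion rests on the documents' own timing and needs no assumed figure.

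The size does rest on assumptions. It is zero if MFC leaves coverage unchanged. For assumed shifts of 5 to 10 points it runs from near zero to 0.053 SD, or about half a standard error at 200 per arm. At the upper, unanchored shift of 16 points it reaches 0.084 SD. The sign depends on relationships the documents do not describe. This should be changed because it is avoidable and the remedy is cheap, not because a large distortion is expected.

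**What to change.** In both documents, delete the four words that add the 6-month time point, leaving *Medicaid status (yes/no) at birth* as the covariate. Add two words to define the moderator as *family Medicaid status at birth*. Report 6-month Medicaid only as an outcome, or in a sensitivity or mediation analysis labelled as such. State when single-parent household is measured, and take it as of birth if a birth-time source is confirmed.

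Make the change by a dated amendment that gives the reason and says whether outcome data had been seen. Showing results with and without the term, with the birth-only model as the main one, keeps the change transparent.

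The Medicaid change needs no new data. The statistical cost is a possible small loss of precision: in the simulations the standard error without the 6-month term was 0.98 to 1.03 times the standard error with it.

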## Study Procedures

**If you uploaded a separate research protocol document in the 'Research Protocol' page, cite the applicable section and page numbers from that document in the answer boxes below. (If this study is a collaborative UM/VA study please list each procedure that is being conducted and the locations where it is being conducted.)**

1 \* Describe all procedures being performed for research purposes only (these procedures would not be done if individuals were not in the study) and when they are performed, including procedures being performed to monitor subjects for safety or to minimize risks:

Research staff will visit the Sinai Hospital maternity ward on a daily basis. They will receive regular updates from maternity and MFC staff about new births to Baltimore City residents. For approximately one year and a half starting July 15, 2019, all Baltimore City residents who give birth on an odd date at Sinai Hospital will be offered MFC by nurse home visitors employed by [REDACTED]. From July 15, 2019 – January 14, 2021, research staff will approach ALL new mothers (Baltimore City residents giving birth on even or odd dates) within 1-3 days of the birth of the baby, while they are still in the hospital/maternity ward. The researchers will provide mothers with a brief description of the study and a 1-page information sheet (attached). The researchers will request permission to contact the mothers when their infants are approximately 6 months old to schedule the in-home psychosocial interview. During the hospital meeting, the researchers will confirm mothers' contact information and share their own contact information.

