## Waiver of Documentation of Consent

You indicated that a waiver of documentation of consent (verbal/oral consent) is requested.

1 \* Indicate why a waiver of documentation of consent is being requested for the study:

- The only record linking the subject and the research would be the consent document, and the principal risk would be potential harm resulting from a breach of confidentiality.
- The research presents no more than minimal risk of harm to subjects, and involves no procedures for which written consent is normally required outside of the research context.

2 \* Provide a justification/explanation for the choice above:

We have requested to waive written consent given the current social distancing circumstances and COVID-19 precautionary guidelines. At the current time, we will not be meeting with participants in person for their 6-month interview. In order to ensure participants receive consent information prior to their virtual interview, we believe that reading the consent form word-for-word at the start of the interview will be the best way to inform participants and to get their consent.

ID: VIEW4E1C6EF6F5000  
Name: v2\_Waiver of Documentation of Consent

View: v2\_Children (Assent)

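### The models have no calendar term although births straddle the COVID-19 disruption: a modest missed efficiency for the 6-month outcomes, not a bias

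*SAP*

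**What the plan says.** The SAP, and the matching text in the protocol under Sample Size and Data Analysis (item 2), give one covariate list for every model: "Covariates for all models will include the following: Medicaid status (yes/no) at birth and at 6 months", then mother's race/ethnicity, single-parent household and birth complications. Neither list contains birth date, calendar period or interview mode. The moderators do not supply one either: "Exploratory moderators will include infant birthweight, family Medicaid status, and mothers' adverse childhood experiences and adult attachment security".

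On timing, Study Procedures says "From July 15, 2019 – January 14, 2021, research staff will approach ALL new mothers". Under Waiver of Documentation of Consent the protocol explains: "We have requested to waive written consent given the current social distancing circumstances and COVID-19 precautionary guidelines", and adds that 6-month interviews were then not being held in person. Study Procedures describes the replacement by video or phone. No section gives a date for the start of the disruption or a figure for its effect on any outcome.

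Under Justification, Objective, & Research Design, assignment follows the infant's birth date: the programme is offered on odd dates and not on even dates. The SAP is dated July 18, 2023, after recruitment was due to end.

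**The concern.** The 6-month outcomes are emergency-room use and overnight stays, use of community resources and child care, maternal wellbeing and the home environment. Social distancing could plausibly shift any of them. The way they were measured changed as well, since the HOME assessment relies on an assistant observing the home.

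If period predicts an outcome and is left out of an ordinary least squares model, its variation stays in the residual and the treatment effect is estimated less precisely than it could be. Birth date would be a safe adjuster: it is fixed before assignment and held for everyone. At stake is some power in a trial whose planned size leaves little to spare.

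**Working it through.** **1. The plan's own figure.** Sample Size and Data Analysis reports "power analyses estimating at least 0.80 power and a significance level of 0.05" and says that "a sample size of 400 (assuming equal groups) will detect small to medium effects in most of the outcomes of interest". It gives no numerical effect size, so 400 can only be solved backwards. With 200 per group and two-sided 0.05, detectable d = (1.960 + 0.842) × √(2/200) = 0.280. Power is 52% at d = 0.2 and over 99% at d = 0.5. The figure is consistent with a small-to-medium effect, and d = 0.28 at 80.0% power is the starting point below.

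**2. How far the births straddle the disruption.** The window holds 550 dates. Assume a cut at 15 March 2020, a 182-day outcome window from birth, and families spread evenly over the dates. The share of each infant's window after the cut is then zero for 11% of dates, partial for 33% and complete for 56%; its mean is 0.72 and its variance 0.146. Moving the cut to 1 March or 1 April gives variances of 0.134 and 0.159.

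**3. Balance between arms.** Of the 550 dates, 281 (51.1%) are odd. With a 19 March cut, 51.2% of dates before and 51.0% after are odd. Exposure share correlates −0.003 with date parity.

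**4. Net gain.** Let the outcome shift by D SD between no and full exposure.
- Variance explained: R² = 0.146 D² / (1 + 0.146 D²).
- Price of k added terms, assuming 8 baseline parameters: a variance factor of 391/(391 − k), which is 391/390 = 1.0026 for one term and 391/385 = 1.0156 for six.
- Effective N = 400 × (1 + 0.146 D²) / factor.

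The window touches seven calendar quarters, so quarter indicators cost six terms. Crediting them with the whole exposure effect, which favours them:

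| D (SD) | R² | One term: net families | Six quarter indicators: net families |
|---|---|---|---|
| 0.1 | 0.15% | about 0 | −6 |
| 0.2 | 0.6% | +1 | −4 |
| 0.3 | 1.3% | +4 | −1 |
| 0.5 | 3.5% | +14 | +8 |

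Example for one term at D = 0.5: 400 × 1.0365 / 1.0026 = 413.5. The two alternative cuts give +12 and +15. If period has no effect, one term takes power from 80.0% to 79.9%.

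Break-even R² is k/391: 0.26% for one term, 1.5% for six quarter indicators and 4.6% for 18 month indicators. A separate indicator for each date leaves the treatment effect inestimable (551 columns, rank 550), because date parity is the allocation.

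**5. A before/after-birth term.** If the shift follows birth before or after the cut (45/55 split on 19 March), R² is 2.2% at 0.3 SD and 5.8% at 0.5 SD. A 3,000-replicate simulation on the actual odd/even calendar gave these powers without and with the term: 78.3% and 78.3% (no shift), 80.0% and 79.8% (0.1 SD), 77.5% and 78.6% (0.3 SD), 76.6% and 79.2% (0.5 SD). If the shift instead follows the date the infant reaches 6 months, the split is about 12/88 and R² is smaller: 0.9% and 2.6% at 0.3 and 0.5 SD.

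**6. Counts.** Poisson models have no residual-variance term. Simulating N = 400 with assumed mean 0.8, dispersion 0.75 and a 50% fall from no to full exposure, the model-based standard error stays at about 0.112 to 0.113. The robust one falls from about 0.146 to 0.143, or 2%.

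**The case against.** The strongest reply is that this is optional tuning. The documents give no period effect or onset date, and actual accrual through the pandemic is not reported, so every gain above is conditional. That stands, and it is why a range is shown.

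Four stronger readings are tempting, and the documents do not support them.
- *The omission biases the comparison.* It does not by design: alternation of dates puts nearly the same share of odd dates on each side of any plausible cut.
- *A chance period imbalance among the interviewed families is a further, uncorrected harm.* The standard error already covers it; counting it separately counts the precision gain twice.
- *Every estimate would become more precise at no cost.* For an outcome with little period shift a term costs slightly more than it returns, quarter or month indicators can lose precision over plausible shifts, and Poisson model-based intervals barely move.
- *All models need the term.* A six-month exposure share has no shown relevance to maltreatment investigations or kindergarten outcomes.

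Timing also matters. A SAP dated July 2023 postdates the last planned 6-month interviews (about July 2021), so a term chosen after seeing results by arm would lose the standing of a pre-specified one.

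**Conclusion.** The point holds as a missed efficiency, limited to the infancy outcomes. The omission, the straddle and the availability of birth date are all in the documents; the size is not. For continuous outcomes, one term is worth about nothing at a 0.1 SD shift, 4 families in 400 at 0.3 SD and 14 at 0.5 SD. For a count that halves, it is worth about 2% of the robust standard error, and nothing visible in a model-based one; the SAP does not say which it will use.

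These figures assume a mid-March 2020 cut, even accrual over the 550 dates and 8 baseline parameters. The balance in step 3 is a property of birth dates. The documents give no enrolment by arm and period, so they neither show nor exclude differential participation among the families who consent at 6 months.

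**What to change.** For the 6-month (infancy) outcomes, add one sentence to the SAP that names a single one-degree-of-freedom birth-date term: either the share of the outcome window falling after a stated date, or birth before/after that date. State the date, and define the window for each outcome.

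Do not use quarter, month or exact-date indicators, for the reasons in step 4. Do not use interview mode, which is settled after assignment.

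Fix the term before outcomes are examined by arm. If they have already been examined, keep the stated covariates for the main analysis and report the adjusted model as a sensitivity analysis.

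The cost is one sentence, no new data and one degree of freedom: about 0.1 to 0.2 points of power if period turns out not to matter.
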